3.2 Hypotheses and tests

We first propose hypotheses regarding relationships between CVD beliefs, information and behaviour that will be tested using data on elicited beliefs and the information experiment, which are summarized in Table 1.

Q1: Are the elicited beliefs interpretable as subjective probabilities?

[H1a] Elicited probabilities have face validity and are consistent with rules of probability.

Tests:

- Use data from section A.
- Face validity: Ask for perceived life expectancy and for perceived chance of living past 80 years. Check whether those variables are positively correlated.
- Monotonicity: Ask for perceived probability of a destructive earthquake in respondent's province within one year and within 10 years and check percentage of respondents for whom the latter reported probability is not smaller than the former.
- Binary complementarity: Ask for perceived probability that there will be a destructive earthquake in respondents' province within the next 10 years and perceived probability that there will NOT be a destructive earthquake during the same period. Check percentage of respondents for whom the probabilities add up to 1. Compute mean sum of those two subjective probabilities and test whether it equals 1.

[H1b] The prevalence of consistency violations varies with education.

Test:

• Regress binary outcome indicating violation of probability rule (monotonicity and binary complementarity) on education level (and possibly other characteristics).

1 au	ie i Overview of fisk perceptions survey module				
Sect	ion	Treatment group	p Control group		
A.	Training questions	A_{T}	A _C		
B.	Perceived average CVD risk (base rate)	B_{T}	B_{C}		
C.	Information on average CVD risk	C_{T}			
D.	Perceived personal CVD risk (prior)	D_{T}	D_{C}		
E.	Information on personal CVD risk	E _T			
F.	Perceived personal CVD risk (posterior)	F _T			
G.	Information on CVD risk if reduce risk factor exposure	G _T			
Н.	Perceived personal CVD risk if reduce risk factor exposure	H_{T}	H_{C}		

Table 1 Overview of risk perceptions survey module

Note: CVD risk is the probability of having a heart attack or stroke within the next 10 years. We also ask about the probability of getting diabetes within the next 10 years. Sections B, D & F also ask about perceptions of life expectancy and probability of survival to 80.

Q2: Do elicited beliefs incorporate information about objective risks?

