D _T , D _C	Effect of base rate CVD risk information on perceived personal CVD risk.

F_T, D_C	Effect of information base rate + personal CVD risk information on
	perceived personal CVD risk.
H _T , H _C	Effect of base rate + personal + reduced risk factor CVD risk information
	on perceived personal CVD risk if reduced risk factors.
F_T - H_T , D_C - H_C	Effect of information on change in CVD risk if reduced risk factors on
	perception of that change.

- Using the treatment group only, we obtain an alternative estimate of the effect of being informed of predicted personal CVD risk on perceived personal CVD risk by regressing the latter on an indicator of whether it is measured prior to or after receiving personal risk information. That is, a simple before-after comparison: $p_i = x_i \beta + \gamma 1 (p_i = F_{Ti}) + u_i$, $p_i = D_{Ti}$ or F_{Ti} .
- We will run similar regressions to test for updating of confidence about reported risks and worry about CVD risk. See the last point under [H5a] on the relevance of the impact of information on belief confidence.

[H3b] Individuals who are exposed to the information intervention do not simply memorize numbers and percentages they are told in the treatment, but incorporate the information to update beliefs about event likelihoods related to CVD risks.

Test:

• Estimate the correlation between the prior-posterior change in perceived life expectancy and the prior-posterior change in perceived 10-year CVD risk. A negative correlation means that individuals update their life expectancy in a direction consistent with their revision to perceived personal CVD risk. For example, if the perception of CVD risk is raised, then life expectancy is reduced. We will repeat the same exercise for life expectancies conditional on experiencing a heart attack/stroke. As survival probabilities conditional on a CVD event are independent of CVD risk, a coefficient of zero is consistent with Bayesian updating. We use the same beliefs as described in [H3b] to test for updating following the provision of both base rate and personal CVD risks and the provision of only personal CVD risks.

[H3c] Updating of beliefs is heterogeneous with respect to education, predicted CVD risk, confidence about CVD risk estimates and worry about CVD events.

Test:

• Repeat regression (3.1) allowing λ to vary with the stated characteristics.

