Section 2 asks the respondent to report the chance that someone of the same age and gender will have a heart attack or a stroke within ten years. This is interpreted as the respondent's perception of the CVD base rate. Section 3, as well as Sections 5-7, is completed only by respondents in the information treatment group. These sections are described in the next section of this document. In section 4, the respondent is asked to report the chance that she will have a heart attack or a stroke in the next ten years. This is interpreted as the prior belief of personal CVD risk. In Section 8, the respondent is asked to report what her chance of a heart attack or stroke within ten years would be if she were to adopt healthier behaviour, i.e. to quit smoking (if a smoker) and to control blood pressure and weight.

After stating her perceived CVD risk in Sections 2 and 4 (and 6), the respondent is asked how confident she is in her answer on a five-point scale ranging from 1 (not at all confident) to 5 (extremely confident).

Respondents are likely to differ in how certain they are that the stated probability is close to the actual probability of having a heart attack or a stroke. Moreover, in Section 4 (and 6) the participant is asked how worried she is about having a heart attack or a stroke on a five-point scale ranging from 1 (not at all worried) to 5 (extremely worried).

5. Interventions

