5.2 Information on CVD risk

Information provided

Respondents randomly allocated to this treatment group will receive information on the predicted probability of having a heart attack or stroke within 10 years. The predictions will be obtained from the Globorisk tool (Ueda et al 2017). The reasons for using this algorithm are given in the next sub-section. All information will be provided within the risk perceptions module of the survey. Only this module will differ across the two treatment groups (information and lottery) and the control group. Information obtained from earlier modules will be retrieved automatically and used to make predictions of CVD risk consistent with the risk factor profile of the respondent in the information treatment group.

Three types of information on CVD risks will be provided to those in the respective treatment group: a CVD base rate, a personalized CVD risk and an optimal CVD risk. The CVD base rate will be predicted from the respondent's age and sex only. This information will be provided immediately after the respondents are asked to report the chance of someone of their age and gender having a heart attack or a stroke within ten years, and immediately before being asked to report the chance that they will have a heart attack or stroke within that period. The respondents will be presented with the information both as a chance of X in 100 and as the number of people (X) out of 100 the same age and sex as the respondent that doctors would expect to have a heart attack or stroke within ten years.

After reporting their own chance of having a heart attack or stroke within ten years, the respondents in the treatment group will be told the risk for someone with the same age, sex, smoking status, BMI and blood pressure as them. Each respondent will not be told that this is their own chance of having a heart attack or stroke. Rather, if the respondent is female, she will be told that out of 100 women her age, with the same

weight and blood pressure as her, and who (don't) smoke like her, doctors would expect X to have a heart attack or stroke within 10 years. Analogous information will be provided to male respondents. After being given this information, the respondent is asked again to report their 10-year CVD risk. This is interpreted as the posterior belief (after the provision of personalized information).

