UPecon survey												Х	Х		
monitoring															
Survey firm delivers														Х	
follow-up data															
Analysis of follow-up data														Х	Х
Write papers															\rightarrow

Our intention is to field the baseline survey in August-September 2017. As explained above, the information intervention will form part of the risk perceptions module of the baseline survey. The module used with information treatment group respondents will differ from that used with the lottery treatment group and the control group. The module will be positioned in the survey after physical measurements of blood pressure and BMI in order that these measures can be used in the calculation of the predicted CVD risk that will be revealed to the treatment group respondents.

Those allocated to the lottery intervention will be told of their chance to enter the lottery at the end of the baseline survey and given a voucher to be exchanged for a lottery ticket at a specific RHU/CHC. The chance to enter the lottery expires one month after the baseline in order that we observe a sufficiently long period between risk assessment at the designated facility and the follow-up survey.

The follow-up will be conducted around 6-7 months after the baseline in March-April 2018. This will provide sufficient time to observe the effect of medications prescribed at initial contact with the RHU/CHC and to assess whether follow-up consultations are conducted for the target populations, as stipulated by the PhilPEN protocol.

7. Outcomes

We will estimate effects on predicted CVD risk, risk factors, health care management of CVD, CVD-related behaviours, perceptions of CVD risk and knowledge of CVD risk factors.

Principal outcome

The principal outcome for both interventions is mean 10-year risk of a heart attack or stroke predicted using the office version of Globorisk (Udea et al 2017).

i) Mean 10-year risk of CVD event (Globorisk prediction)

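### Only the information arm is asked for its personal CVD risk twice, so F_T v D_C and the before-after estimate include in full any mean shift from being re-asked

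*Combined protocol and SAP*

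**What the plan says.** Section 4 describes a risk perceptions module of eight sections, lettered A to H in Table 1 of Section 3.2. Every arm reports its personal 10-year CVD risk once, in section 4 (D). For the rest, "Section 3, as well as Sections 5-7, is completed only by respondents in the information treatment group". Section 6 of the module (F) repeats the personal-risk question. Section 5.2 of the protocol describes it, following disclosure of the personalised risk: "After being given this information, the respondent is asked again to report their 10-year CVD risk". Table 1 accordingly has F_T but no F_C. The confidence rating follows module sections 2, 4 and 6, and the worry rating follows 4 and 6, so these items are also repeated in the information arm only.

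The lottery arm does not fill the gap. Section 6 (Timeline) states: "The module used with information treatment group respondents will differ from that used with the lottery treatment group and the control group". No arm is asked twice without information in between.

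H3a lists the contrast F_T, D_C with the label "Effect of information base rate + personal CVD risk information on" perceived personal risk. It continues: "Using the treatment group only, we obtain an alternative estimate of the effect of being informed of predicted personal CVD risk", to be obtained by "regressing the latter on an indicator of whether it is measured prior to or after receiving personal risk information". This is a comparison of D_T with F_T, and similar regressions are planned for confidence and worry. The first stage of the H4a instrumental-variable model regresses post-information perceived risk on the treatment indicator, which for controls can only be D_C.

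**The concern.** F_T v D_C compares a second answer with a first. D_T v F_T compares a second answer with a first in the same people, without a comparison group. If answering the same question again within one module moves the mean (through reconsideration, practice with the dots tool or a wish to appear responsive), both estimates count that movement as information. Because both carry the same term, agreement between them is no corroboration.

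What is at stake is the first link in the theory of change. Section 3.1 says the belief data will show at which stage the chain failed if behaviour does not change. That needs a clean estimate of how far personal information moves beliefs, and outcome xx in Section 7 is that estimate. The H4a estimate divides by the same first stage, and H5b uses the confidence responses.

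**Working it through.** **Structure.** Let b be the mean shift from being re-asked. Then:

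- E[F_T] − E[D_C] = effect of base-rate plus personal information + b
- E[F_T] − E[D_T] = effect of personal information + b
- E[D_T] − E[D_C] = effect of base-rate information only (first answers in both arms, no b)

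A simulation with 1,000,000 per arm agrees. With no information effect and b = 0.1 SD, the two planned estimates are 0.100 and 0.099 SD. With a true effect of about 0.09 SD and b = 0.1 SD, both are 0.191. If the H4a reduced form is unchanged, a first stage of 0.191 in place of 0.091 scales the instrumental-variable estimate by 0.091/0.191 = 0.48.

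**Inputs from the plan.** The arm sizes are 299 and 1,361 (Table 6, binary column, the size adopted). ICC 0.1 and 10 per cluster give a design effect of 1 + 9 × 0.1 = 1.9. Significance is 5%, taken as two-sided. The plan states no figure for the belief contrasts, and Section 7 says power could not be calculated for outcomes xix to xxi. The Table 6 sizes for mean CVD risk can be checked: 2 × 7.849/0.04 × 1.9 × 0.64/0.36 = 1,326 against 1,306, and for the information arm 1/(1/238.6 − 1/1,306) = 292 against 287. Both are within 3%.

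**Assumptions, not in the documents.** SD of perceived risk 20 points (range 15 to 25), within-person correlation r = 0.6 (range 0.4 to 0.8), drift of 2 or 3 points, no covariates, and no clustering of within-person changes.

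**Standard errors.**

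- F_T v D_C: 20 × √(1.9 × (1/299 + 1/1,361)) = 1.76
- Before-after, paired: 20 × √(2 × (1 − 0.6)/299) = 1.03
- Before-after, stacked with ordinary errors that ignore pairing: 20 × √(2/299) = 1.64, while the true sampling SD is still 1.03

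**Chance of a significant result with no information effect (SD 20, r = 0.6).**

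| Analysis | drift 0 | drift 2 | drift 3 |
|---|---|---|---|
| F_T v D_C | 5% | 21% | 40% |
| Before-after, paired | 5% | 49% | 83% |
| Before-after, stacked, ordinary errors | 0.2% | 12% | 42% |

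The last row uses the critical value 1.96 × 1.64 with sampling SD 1.03.

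**Sensitivity at a 2-point drift.** With SD 25 or 15, the between-arm rate is 15% or 33%, the paired rate 34% or 73%, and the stacked rate 6% or 30%. With r = 0.4 or 0.8 at SD 20, the paired rate is 35% or 78%. With no clustering, the between-arm rate is 35%. A downward drift gives the same rates and could equally mask a real upward effect.

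**The case against.** The strongest reply is that Q3 does not rest on mean shifts alone. Equation (3.1) relates each revision to the signed gap between prediction and prior. H3d separates good news from bad. H3b relates revisions of CVD risk to revisions of life expectancy. A uniform drift does not predict movement in opposite directions according to the news. This stands: a reader might infer that no positive finding could be told apart from re-asking, and that is more than the documents support. Equation (3.1) does have a separate weakness. In the simulation, with single-answer reliability assumed at 0.6 and no information effect, its slope was about 0.30, because the noisy prior enters both sides.

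Further points stand:

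- No drift is documented, and its size, the SD and the correlation are all assumed.
- A reader might infer that the before-after standard errors are wrong. H3a gives only a mean equation and no variance estimator. Person- or barangay-clustered errors would handle the pairing without a person term.
- The F − H contrasts and the first H2i test are asymmetric, but a reader should not infer a known bias. H follows F in the information arm and D in controls, so drift may partly cancel, and no net bias has been shown.
- Table 6 gives follow-up sizes, whereas D and F are baseline answers. The somewhat larger baseline numbers would raise the rates slightly.

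None of this removes b from F_T v D_C or from D_T v F_T.

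**Conclusion.** The concern holds for the mean contrasts F_T v D_C and D_T v F_T, the parallel confidence and worry regressions, and the H4a first stage. Each includes any re-asking shift in full. The plan has neither a re-asked comparison group nor a stated assumption that the shift is zero; H3b addresses memorised numbers, which is a different matter. The tabulated rates illustrate sensitivity under assumed inputs and do not estimate the trial's error rate. The paired and stacked rows are alternatives, because the plan does not say which errors it will use.

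It would be wrong to extend the point to the main results. D_T v D_C compares first answers. The principal outcome is predicted risk at follow-up, and the H5a reduced form does not use F as an outcome; there the repeated question is simply part of the delivered module.

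**What to change.** Repeat the personal-risk, confidence and worry items at position F, after neutral text, without information and before H. Do this in a random subset of controls, or equally in the control and lottery modules. Changing only the whole control module would make it differ from the lottery module and disturb that comparison.

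Then use F_T v F_C between arms. Replace the before-after estimate by (F_T − D_T) v (F_C − D_C) on within-person differences, with barangay-clustered errors. Report H2i and the F − H contrasts with F in both arms as a sensitivity analysis. In the simulation (no information effect, b = 0.1 SD) the two replacement estimates are 0.000 and −0.001. A re-asked group would also show the slope that (3.1) produces without information.

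The cost is three tablet items, about one minute for those respondents, and no extra participants. Some precision is lost relative to the single-arm comparison. With 299 re-asked controls and the assumptions above, the SE of the difference in changes is 20 × √(0.8 × (1/299 + 1/299)) = 1.46, against 1.03. A neutral re-ask may also not reproduce the re-asking effect exactly.

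If the items cannot be fielded, state the assumption of no re-asking effect, stop labelling F_T v D_C as purely an effect of information, and specify how the before-after errors allow for pairing.
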